#### **6.2. Visit 2 (approximately 4 weeks after Visit 1) – Month 1 of treatment**

- Adverse event review and urine pregnancy test
- Keloid observation and clinical assessment
- Photography and caliper measurements – (same as baseline)
- Dispense medication

#### **6.3. Visit 3 (approximately 4 weeks after Visit 2) – Month 2**

- Adverse event review and urine pregnancy test
- Keloid observation and clinical assessment
- Photography and caliper measurements – (same as baseline)
- Dispense medication

#### **6.4. Visit 4 (approximately 4 weeks after Visit 3) – Month 3**

- Same as above, plus repeat CBC, CMP, lipid panel

#### **6.5. Visit 5 (approximately 4 weeks after Visit 4) – Month 4**

- Same as above and urine pregnancy test

## 6.6. Visit 6 (approximately 4 weeks after Visit 5) – Month 5

- Same as above and urine pregnancy test

## 6.7. Visit 7 (approximately 4 weeks after Visit 6) – Month 6 – Final Study Visit

We will ask participants to return to the hospital to undergo post-treatment procedures, conclude the study data collection and disenrollment processing.

- Vital signs, weight, and lab work to ensure safety or rule out systemic infection or effects (CBC, CMP, lipid panel)
- Update medical history, concomitant medications, focused physical examination, and
- Evaluation of medication compliance
- Final adverse event review
- Keloid observation and clinical assessment
- Photography and caliper measurements – (same as baseline)

## 6.8. Summary Visit Schedule

Event	Screening & Baseline Visit 1	Visit 2 (V1 +1m)	Visit 3 (V2 +1m)	Visit 4 (V3 +1m)	Visit 5 (V4 +1m)	Visit 6 (V5 +1m)	Visit 7 (V6 +1m)
Consent	X						
Vital signs	X	X	X	X	X	X	X
Height (V1 only) and weight	X						X
CLOX exam	X						
Urine HCG, monthly	X	X	X	X	X	X	
Labs: CBC, CMP, and lipid panel	X			X			X
History	X						X
Physical Exam	X						X
ConMed Review	X	X	X	X	X	X	X
Keloid Observed		X	X	X	X	X	X
Photo and Caliper		X	X	X	X	X	X
Dispensing Rx		X	X	X	X	X	
Medication Instructions and phone calls weekly between V1-V2 and at midpoint between V2-7 for compliance monitoring		X	X	X	X	X	
AE Review			X	X	X	X	X
Questionnaires		X					X
Disenrollment							X

## 7. Statistical Plan

### 7.1. Statistical Methods

For all analyses, the statistical threshold for significance will be set at  $p<0.05$ .

Keloid surface area and height data will be analyzed using ANOVA for repeated measurements using a

model similar to that described for the analysis of the preliminary data (see INNOVATION, above) with the addition of a random effect for subject (47). This analysis can be modified to include between-subject factors if such factors (sex, race, etc.) are identified for investigation.

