### **Objectives:**

1. To compare the effect of topical RAPA 8% ointment to treat established keloid versus untreated keloid
2. To test whether regression of surface area occurs after 6 months of treatment
3. To test whether regression of height of treated keloid occurs after 6 months

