## 3. Study Design

### **3.1. Subjects**

We will screen up to 20 persons ages 18-75 without diabetes or unstable, chronic diagnoses. We intend to complete 5 subjects achieving 6 months of treatment with topical RAPA. Refer to Section 4, Inclusion/Exclusion Criteria.

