### **3.2. General Design**

Our pilot trial will use daily 0.5-1.0ml applications of 8% RAPA in a petrolatum vehicle to treat established keloid lesions in 5 persons with at least 2 chronic keloids in similar body regions (greater than 1-year duration). Treatment will be applied once daily for 6 months. One keloid will receive 8% RAPA ointment and the other keloid will receive petrolatum-only ointment as a control. Surface areas and height of keloids will be monitored pre- and post-treatment to evaluate responses.

We will measure keloid surface area and height changes pre-treatment and thereafter on a monthly basis using standardized digital photography with a tripod-mounted 8MP Canon S5is camera and calipers to measure keloid height (37).

Surface areas of all photographed lesions will be measured with Image J (<http://rsbweb.nih.gov/ij/index.html>), a public image-processing program that we used to analyze our preliminary data and will use the same approach in this study.

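### Section 7.1 ties no test to the 6-month objectives, and the common readings of its repeated-measures ANOVA give a diluted or invalid test

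*Combined protocol and SAP*

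**What the plan says.** Section 2 compares RAPA-treated with control keloids and then fixes the horizon: "To test whether regression of surface area occurs after 6 months of treatment", with a matching objective for height. Section 3.3 gives change in area and height as the primary outcome, without a time point.

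The design is paired. Section 3.2 states: "One keloid will receive 8% RAPA ointment and the other keloid will receive petrolatum-only ointment as a control". On timing it states: "We will measure keloid surface area and height changes pre-treatment and thereafter on a monthly basis". On size, Section 3.1 states: "We intend to complete 5 subjects achieving 6 months of treatment with topical RAPA".

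Section 7.1 is the whole statistical plan. It begins "For all analyses, the statistical threshold for significance will be set at" p<0.05, and continues "Keloid surface area and height data will be analyzed using ANOVA for repeated measurements". The details are delegated to a "model similar to that described for the analysis of the preliminary data (see INNOVATION, above"), to which a random subject effect is added. Section 1.2 (Innovation) covers mTOR biology and treatment background and describes no statistical model. The citation for the random effect is number 47, while the reference list ends at 23.

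**The concern.** A repeated-measures ANOVA on two keloids and seven visits yields several p-values: treatment, visit, and treatment by visit. Their error terms depend on choices that the plan leaves open. None of these tests is, by default, the 6-month comparison in the objectives. The treatment term averages over visits. The interaction term asks whether the two profiles differ in any way at all.

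With five completers the choice matters. One reading makes false positives common, another dilutes a real effect that builds over time, and a third inflates the interaction test when keloids change at different rates. Because the plan does not say which term carries the conclusion, the choice could also be made after the results are seen.

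**Working it through.** The plan states no power, effect size or variance, so there is no figure of its own to reproduce beyond the nominal 0.05.

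**Inputs from the protocol.** 5 participants (3.1); 2 keloids each, one per treatment (3.2); 7 measurements, baseline plus Months 1 to 6 (3.2; Section 6.1.2 lists photography and calipers at baseline).

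**Assumed inputs.** The unit is the noise SD of the RAPA-minus-vehicle difference at one visit. I vary two quantities in that unit: the SD of the keloids' starting-size difference, and the SD of the difference in their 6-month change (the slope SD). Type I errors and powers below are simulated, with at least 40,000 runs per setting in the runs for (b) and (c).

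**(a) Literal reading: random subject intercept only.**
- Observations: 5 × 2 × 7 = 70. Residual df: 70 − 14 treatment-by-visit means − 4 for subjects = 52.
- Let σe be one keloid's noise SD and σk the SD of keloid starting sizes within a participant. The ratio σk/σe is the same whether taken per keloid or on differences.
- Under no effect, the expected treatment mean square is σe² + 7σk².
- The keloid variation (4 df) is pooled into the residual, whose expected value is [4(σe² + 7σk²) + 48σe²]/52 = σe² + 0.54σk².
- At σk = σe the two are 8 and 1.54, a ratio of 5.2 where a valid test needs 1. At σk = 3σe they are 64 and 5.85, a ratio of about 11.
- Simulated type I error of the treatment main effect: about 39% to 57% over this range. The interaction test under this reading reaches at most about 7.5%.

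**(b) Textbook two-within-factor version, treatment main effect, baseline as a response level.** Each factor below is the visit-averaged effect divided by the Month-6 effect.

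| Shape of effect | Mean over Months 0–6 |
|---|---|
| Linear | (0+1+…+6)/(7×6) = 0.50 |
| Full from Month 1 | 6/7 = 0.86 |
| Linear to a plateau at Month 3 | 5/7 = 0.71 |
| Quadratic, accelerating | 91/(7×36) = 0.36 |

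Without baseline, the linear factor is 21/36 = 0.58.

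Power, for a linear effect with mean 6-month difference 3 and slope SD 1: the visit-averaged effect is 1.5. Its variance between participants is (starting-size SD)² + 0.25 + 1/7.

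| Starting-size SD | Standardised effect | Power |
|---|---|---|
| 0 | 1.5/0.63 = 2.4 | 97% |
| 1 | 1.5/1.18 = 1.3 | 57% |
| 3 | 1.5/3.06 = 0.49 | 14% |

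**(c) Textbook version, treatment-by-visit F on 6 and 24 df.** The critical value is 2.508. If keloid-specific slopes swamp the noise, the statistic behaves as F(1,4), and P(F(1,4) > 2.508) = 18.8%, the ceiling.

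| Slope SD | Uncorrected type I error |
|---|---|
| 1 | 5.5% |
| 2 | 8% |
| 4 | 13% |
| 8 | 17% |

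The Greenhouse-Geisser version gave 0.8% to 5.3% and was most conservative, about 1%, where slopes vary little. The inflation needs rates that differ between a participant's two keloids. If both share one rate, the uncorrected error is 4.8%.

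**(d) Paired Visit 1 to Visit 7 change.** Type I error was about 5% throughout (4.8% to 5.2%). In the power scenario of (b), the variance is 1 (slope) + 2 (noise at two visits) = 3, so the standardised effect is 3/√3 = 1.73. Power is 82% whatever the starting-size difference. A test on the slope over all visits has 90%.

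**The case against.** The strongest reply is that the plan does not define the model, so no one of these error rates belongs to it. A repeated-measures model can supply a Month-6 contrast, and the analysts may have intended one. The description may also exist: Section 7.1 speaks of the preliminary-data analysis, and part of the text at the end of Section 1.3 was not available to me. I therefore cannot say that no model is given anywhere.

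Other parts of the reply also stand:
- Section 3.3 speaks of change, and Section 6.1 normalises flattening to the pre-treatment height. If change scores are analysed, baseline is not averaged in. The linear factor is then 58%, and visit-averaged change has 67% power whatever the starting sizes.
- A Greenhouse-Geisser correction answers most of the type I complaint in (c). In the power scenario of (b), the interaction test has 78% power corrected and 95% uncorrected, against 82% for the paired contrast. At that slope SD the uncorrected error is only 5.5%.
- The main effect's 57% power depends on a starting-size SD of 1. At SD 0 it has 97% and beats the paired contrast. SD 0 is unlikely, because Section 4.1 asks only for a similar body area and does not match keloids on size.
- This is a small pilot, and Section 1.5 foresees comparing areas over time, which a profile analysis does.

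The reply does not dispose of the gap. No test is linked to 6 months, and each common reading examined has a different weakness.

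**Conclusion.** The point holds as a fault of specification with real consequences. The literal reading has a badly invalid treatment test (about 39% to 57% type I error) if starting sizes differ by 1 to 3 noise SDs. The textbook reading dilutes an effect that builds over time, to half if it is linear with baseline included. Its uncorrected interaction test runs from 5.5% to 17% over slope SDs of 1 to 8.

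A reader might infer more than this, and the documents do not support it:
- That repeated-measures ANOVA cannot address Month 6. It can, if the contrast is named.
- That the trial's type I error is 19%. That is a ceiling, and it needs one particular error term, no correction, and dominant slope differences between a participant's keloids.
- That any effect is halved. The factor ranges from 0.36 to 0.86 with its shape.
- That a sphericity correction is useless. It holds the error at or near 5%, at the price of conservatism when slopes vary little.

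All variance ratios are assumptions, because the protocol gives none. The missing link to Month 6 in Section 7.1 does not depend on them.

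**What to change.** In Section 7.1, state for each measure that the primary analysis is the within-participant RAPA-minus-vehicle difference in change from Visit 1 to Visit 7. Report it with a 95% CI and a paired t-test on n−1 df. Keep the per-keloid slope over all seven visits and the repeated-measures model as supporting analyses. Give that model a keloid-within-subject term, and apply a sphericity correction to any omnibus test. Write the model out in 7.1 and correct the cross-reference and the citation.

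The cost is wording only, since both visits are already scheduled. The downside is that intermediate visits enter only the supporting analyses. If the effect plateaus at Month 3, the paired contrast has 82% power, against about 90% for the corrected interaction test and 92% for visit-averaged change. Nor does the change make five pairs informative about modest effects: 80% power needs a standardised paired difference of about 1.68, so the interval should carry the interpretation.

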## **8. Safety and Adverse Events**

### **8.1. Definitions**

#### **8.1.1. Adverse Event (AE)**

In general, AE is used very broadly and encompasses physical and psychological harms and includes:

Any untoward or unfavorable medical occurrence in a human subject, including any abnormal sign (for example, abnormal physical exam or laboratory finding), symptom, or disease, temporally associated with the subject's participation in the research, whether or not it is considered related to the subject's participation in the research.

Intercurrent illnesses or injuries should be regarded as adverse events. Abnormal results of diagnostic procedures are considered to be adverse events if the abnormality:

- results in study withdrawal
- is associated with a serious adverse event
- is associated with clinical signs or symptoms
- leads to additional treatment or to further diagnostic tests
- is considered by the investigator to be of clinical significance

#### **8.1.2. Serious Adverse Event (SAE)**

Adverse events are classified as serious or non-serious. A serious adverse event is any AE that:

- results in death;
- is life-threatening (places the subject at immediate risk of death from the event as it occurred);
- results in inpatient hospitalization or prolongation of existing hospitalization;
- results in a persistent or significant disability/incapacity;
- results in a congenital anomaly/birth defect; or
- based upon appropriate medical judgment, may jeopardize the subject's health and may require medical or surgical intervention to prevent one of the other outcomes listed in this definition (examples of such events include allergic bronchospasm requiring intensive treatment in the emergency room or at home, blood dyscrasias or convulsions that do not result in inpatient hospitalization, or the development of drug dependency or drug abuse).

#### **8.1.3. Unanticipated Problems Involving Risk to Subjects or Others (UPIRSO)**

Any incident, experience, or outcome that meets all of the following criteria:

- Unexpected in nature, severity, or frequency (i.e. not described in study-related documents such as the IRB-approved protocol or consent form, the investigators brochure, etc.)
- Related or possibly related to participation in the research (i.e. possibly related means there is a reasonable possibility that the incident experience, or outcome may have been caused by the procedures involved in the research)
- Suggests that the research places subjects or others at greater risk of harm (including physical, psychological, economic, or social harm).

#### **8.1.4. Adverse Event Reporting Period**

The study period during which adverse events must be reported is normally defined as the period from the initiation of any study procedures to the end of the study treatment follow-up. For this study, the study treatment follow-up is defined as 30 days following the last administration of study treatment.

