## Study Summary

Title	Effect of Topical Rapamycin Ointment on Keloid Regression: A pilot study in human subjects
Protocol Number	HSC20190291H
Phase	Pilot
Methodology	For each participant, one keloid will be treated with topical RAPA ointment while the second keloid will serve as an untreated control. 8% RAPA ointment will be applied to the 'treatment' keloid and the second receives petrolatum-only vehicle, to allow each subject to be his/her own control.
Study Duration	7 months including screening and post treatment follow up
Study Center(s)	Audie L. Murphy VA Hospital
Objective	1. To test whether topical rapamycin regresses established keloids in humans by measuring surface area and height changes in the scar over time (6 months) 2. To test safety of product and feasibility of conduct for future clinical trial
Number of Subjects	Screen up to 20 participants to achieve 5 completers
Inclusion Criteria	1. Age 18-75 years old with at least 2 keloid scars (extant at least 1 year) in similar body locations that are easy to reach to apply ointment 2. Subjects will be in good health with all chronic diseases (hypertension, coronary artery disease, etc.) clinically stable 3. Cognitive functioning ( $\text{CLOX1} \geq 10$ and $\text{CLOX2} \geq 12$ ) sufficient to provide informed consent and be able physically to apply QD ointment to affected area 4. Able to attend monthly clinic visits for 6 months
Exclusion Criteria	1. Diagnosis of diabetes 2. Exclusionary medications: systemic steroid or immunosuppressant therapy within past 6 months or local area steroid treatment within 3 months 3. History of allergy to rapamycin or petrolatum-based products
Study Product, Dose, Route, Regimen	8% rapamycin in petrolatum ointment vs. vehicle only
Duration of administration	6 months, once daily
Statistical Methodology	Keloid surface area and height data will be analyzed using ANOVA

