#### **8.1.6. Abnormal Laboratory Values**

A clinical laboratory abnormality should be documented as an adverse event if any one of the following conditions is met:

- The laboratory abnormality is not otherwise refuted by a repeat test to confirm the abnormality
- The abnormality suggests a disease and/or organ toxicity
- The abnormality is of a clinically significant degree requiring active management; e.g. change of dose, discontinuation of the drug, more frequent follow-up assessments, further diagnostic investigation, etc.

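### AE reporting runs to 30 days after the last application, but no contact is scheduled after Visit 7, so most of that window has no solicited AE question

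*Combined protocol and SAP*

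**What the plan says.** Section 8.1.4 (Adverse Event Reporting Period) describes "The study period during which adverse events must be reported" as running from the first study procedure to the end of treatment follow-up, and then fixes that end: "For this study, the study treatment follow-up is defined as 30 days following the last administration of study treatment". The Study Summary is consistent with this. It gives 6 months of administration and a total duration of "7 months including screening and post treatment follow up".

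The visit plan stops earlier. Section 6.7 makes Visit 7 (Month 6) the last study visit, at which staff "conclude the study data collection and disenrollment processing" and carry out the "Final adverse event review". The Section 6.8 schedule marks disenrollment at Visit 7 and has no later column. Section 5.4 places the phone calls weekly between Visits 1 and 2 and at the midpoints between Visits 2 and 7. Section 8.2 has staff ask about AEs whenever they are in contact with the participant. It also requires recorded events to be followed to an outcome, and possibly related serious events after the study period to be recorded.

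**The concern.** One part of the protocol makes a 30-day post-treatment period mandatory for AE reporting, and another part closes out the participant before that period has run. Because AEs are solicited at contacts and no contact follows Visit 7, a site that follows the schedule exactly will not ask about new events in most of the window.

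Safety is at stake here, not efficacy. The second objective in the Study Summary is the safety of the product and the feasibility of a future trial. Section 3.4.1 lists discomfort, itching, redness, irritation and rash as the expected topical effects. Such mild events tend to be recorded when someone asks and to go unmentioned when nobody does. With 5 completers planned, the safety description rests on a few individual accounts. A report stating that AEs were collected to 30 days after treatment would imply more active ascertainment than the schedule provides.

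**Working it through.** **Inputs**
- Follow-up length: 30 days after the last application (Section 8.1.4).
- Visit spacing: about 4 weeks, with six intervals from Visit 1 to Visit 7 (Sections 6.2 to 6.7).
- Visit 7 is also labelled Month 6, so both 28-day and calendar months are shown.
- Calls: 3 weekly calls in the first month (Section 6.1.2) and one at each of the 5 midpoints between Visits 2 and 7 (Section 5.4).
- Day of last application: not stated. Assumption: the day of Visit 7 or the day before, since use is once daily for the study's duration (Section 5.3) and Visit 7 is post-treatment, with nothing dispensed (Sections 6.7 and 6.8).

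**Step 1: does the stated duration include the follow-up month?** Screening, baseline and first application all occur at Visit 1 (Section 6.1.2), so screening takes no separate month. Six months plus 30 days is 6 × 30.4375 + 30 = 212.6 days. Seven months is 7 × 30.4375 = 213.1 days. The two agree, so the month is in the stated duration but has no procedure in it.

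**Step 2: contacts before and after Visit 7.** With Visit 1 as day 0, Visit 7 is day 6 × 28 = 168.
- Weekly calls: days 7, 14, 21.
- Midpoint calls: days 42, 70, 98, 126, 154.
- Visits: days 28, 56, 84, 112, 140, 168.
- Total: 3 + 5 + 6 = 14 contacts, never more than 14 days apart.
- After day 168: 0 contacts.

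**Step 3: days without a solicited question.** Uncovered days = (day of last application + 30) − day of Visit 7.

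| Visit 7 | Last application | Window ends | Uncovered days | Share of reporting period |
|---|---|---|---|---|
| Day 168 | Day 168 | Day 198 | 30 | 30/198 = 15.2% |
| Day 168 | Day 167 | Day 197 | 29 | 29/197 = 14.7% |
| Day 183 | Day 183 | Day 213 | 30 | 30/213 = 14.1% |
| Day 183 | Day 182 | Day 212 | 29 | 29/212 = 13.7% |

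The uncovered days depend only on the gap between the last application and Visit 7, not on how a month is counted. If dosing ended 7 days before Visit 7, the figure is 30 − 7 = 23 days.

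**Step 4: when a closing call would fall.** 168 + 30 = day 198, or 183 + 30 = day 213. Both lie within 213.1 days.

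These are shares of time, not estimates of missed events. The documents give no rate of reactions arising after treatment stops.

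**The case against.** The best defence is that Section 8.1.4 sets a reporting duty and not a questioning schedule, and that other routes serve that duty. Section 8.3 documents qualifying events brought by the participant or by treating staff. Section 5.1.1 has participants told to report allergic symptoms, including rash. Section 9.3 draws on medical records. Section 8.2 covers open events and later related serious events. Nothing in the documents suggests that new reactions begin after a topical product is stopped, and only about 5 people complete.

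Much of this stands. It confines the gap to active questioning about new, non-serious events and keeps the point small. It does not close the gap, because every route listed for such events is passive, whereas during treatment the plan asks at 14 contacts.

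Three stronger readings are tempting and are not supported.
- A reader might infer that a laboratory abnormality found at Visit 7 would be lost for want of a repeat test. Section 8.1.6 works the other way: one condition for recording an AE is "The laboratory abnormality is not otherwise refuted by a repeat test to confirm the abnormality". An abnormality with no repeat therefore remains an AE, and Section 8.2 requires it to be followed.
- A reader might set the 7-day blood-level result in Section 1.3 against some 168 days of dosing and infer a need for late follow-up. That contrast bears on effects during dosing, which the visits, calls and Month 3 and Month 6 laboratory tests cover.
- A reader might fold in Section 4.4.2, whose exit photographs are worded for withdrawal of consent and not for stops under Section 8.6. That is a separate efficacy matter of little value here, since an early or rash-affected reading says little about 6-month regression.

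One limit remains. Some text next to the reporting section, and the consent pages, are not in the copy reviewed, so contact instructions there cannot be ruled out. The visit sections and schedule, where such a contact would belong, are intact and show none.

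**Conclusion.** The point holds in a limited form. The protocol requires AE reporting for 30 days after the last application and allows time for it, but schedules nothing in which to ask. Assuming dosing runs to Visit 7 or the day before, 29 to 30 of those 30 days have no solicited AE question; the figure falls to 23 if dosing ended a week before Visit 7. It applies to participants who complete treatment. Those stopped early also have no scheduled 30-day contact, but the size of their gap depends on when they are disenrolled.

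The documents do not support saying that safety follow-up ends altogether at Visit 7 or that any particular number of events will be missed. The primary outcome and its analysis are untouched. This is a cheap improvement that makes an existing obligation workable.

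**What to change.** Add one phone AE contact to Sections 6.7 and 6.8, about 30 days after the last application, and complete disenrollment after it. Ask about new events and the status of open ones. Apply it to completers and to participants stopped early, including stops under Section 8.6, provided they have not withdrawn full consent for follow-up; Section 4.4.1 says that such withdrawal may extend to phone contact. Attempt it for participants lost to follow-up. Recording the date of the last application would fix the end of each person's window and remove the assumption used above.

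The cost is 5 calls for the completers plus one per eligible early stopper, at most 20 in all under the screening cap. Each participant stays on study about 30 days longer, to about day 198 to 213. The later date is right at the stated 7 months, so the call should be made promptly once the 30 days are up. No extra visits or participants are needed.
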